5.2 Subject Numbering

If a subject is willing to participate, provides written informed consent/assent, and meets the study eligibility criteria, the subject will be assigned a study subject identification number. This number is comprised of a site number (which is provided by the Sponsor), a sequential subject number and the subject initials.

5.3 Subject Discontinuation Criteria

If possible, every subject should remain in the study until completion of the required follow-up period. However, participation in this study is completely voluntary and a subject can choose to withdraw from the study at any time. Decision to withdraw will not affect or prejudice the subject's continued medical care in any way. A subject will be considered lost to follow-up only after three unsuccessful, documented attempts to contact the subject have been made.

In addition, a subject can be discontinued for any of the following reasons, including but not limited to: the Principal Investigator decides that continuing in the study would not be in the subject's best interest, a subject is noncompliant with the protocol, a subject has a serious reaction to the treatment, a subject develops any of the exclusion criteria during the study period or the study is stopped by the study sponsor.

Confidential and Proprietary

Page 18 of 48

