4 STUDY DESIGN

This is a multi-center, prospective, open-label, single-arm study. Up to 15 study sites will enroll and initiate treatment on up to 107 male and female subjects, ages 16 to 60 years, who present with mild, moderate or severe facial acne at baseline, pass all eligibility criteria and desire laser treatment for their acne. Enrolled subjects will receive [REDACTED] laser treatments on the face [REDACTED]. Subjects will be followed at approximately 10 [REDACTED] days post each treatment (via phone) and at 4 [REDACTED], 12 [REDACTED] and 52 [REDACTED] weeks post-final treatment.

Subjects will be required to undergo a 1 month (30 day) washout period from topical retinoids and other systemic or topical acne medications prior to baseline, and for the duration of the study. If the acne medication is topical, the washout applies to use on the face only. [REDACTED]
[REDACTED]

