7.5 Follow-up of Subjects after AEs/ADEs

All reported AEs/ADEs should be followed until resolution. In the unusual circumstance that an AE/ADE has not resolved by the time of the subject's completion of the study, an explanation will be entered on the appropriate CRF and the subject will be referred to his or her primary care provider (unless specified otherwise by the sponsor). Resolutions of events and all events that result in permanent discontinuation from this clinical trial are to be documented on the appropriate CRFs.

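### Section 5.3 permits removing a subject from the study, without separating this from stopping the laser, for reasons that can relate to failure or tolerance; used early, this can lose the primary lesion count.

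*Combined protocol and SAP*

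**What the plan says.** Section 5.3 opens with a preference for retention: "If possible, every subject should remain in the study until completion of the required follow-up period". It then gives an open-ended list: "In addition, a subject can be discontinued for any of the following reasons". Besides a best-interest decision by the investigator and a sponsor stop, the list includes "a subject is noncompliant with the protocol, a subject has a serious reaction to the treatment" and "a subject develops any of the exclusion criteria during the study period".

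Other sections bear on this:

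- Section 4 describes an open-label, single-arm study of up to 107 treated subjects, with follow-up at 4, 12 and 52 "weeks post-final treatment". It requires a 30-day "washout period from topical retinoids and other systemic or topical acne medications prior to baseline, and for the duration of the study".
- Section 4.2.1 sets the primary endpoint as percent reduction in inflammatory lesion count from baseline to 12 weeks (the sentence is then redacted). Section 11.3 computes it from a baseline and a follow-up count.
- Section 7.5 states "All reported AEs/ADEs should be followed until resolution", and that "all events that result in permanent discontinuation from this clinical trial are to be documented on the appropriate CRFs".
- Section 7.6 requires a pregnant subject to stop treatment and also to leave the study, naming the two acts separately.

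**The concern.** Stopping the laser and stopping observation are different decisions. A serious reaction or a new photosensitising drug can be a sound reason to give no more laser. It is rarely a reason not to count lesions or ask about adverse events afterwards. Section 5.3, as far as it is visible, handles both with one word.

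Some of the listed reasons can be related to outcome. A subject whose acne persists may start a barred acne medication, which is noncompliance. A serious reaction is itself a tolerance outcome. If such subjects leave before the 12-week count, the primary value is missing for reasons connected with how they did. The investigator knows how the subject is responding when using this discretion, and no control arm undergoes the same losses. For safety, the subjects removed after a reaction are among those whose later course matters most.

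**Working it through.** **1. What is discontinued?** The clause does not say. The opening sentence of 5.3 is about remaining in the study, the first listed reason is about continuing in the study, and section 7.5 refers to permanent discontinuation from the trial. Together these support reading it as leaving the study. No visible sentence in 5.3 describes stopping laser while follow-up continues. Section 7.6 shows that the protocol can name the two acts separately.

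**2. When does it matter for the primary endpoint?** The 12-week visit is counted from the final treatment, so the exposed period is the treatment course plus 12 weeks. After that count, the rule cannot affect the primary endpoint.

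**3. Which reasons can relate to failure or tolerance?**

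- *Noncompliance* includes starting an acne medication barred under section 4. Section 12.4.2 already requires deviations to be recorded, although it does not govern whether the subject stays.
- *Serious reaction* is a tolerance outcome by definition.
- *New exclusion criterion* (section 5.1.2). Criterion 10, a facial skin condition, can be a reaction to the laser; it makes a count unreliable only while it interferes with assessment. Criteria 12 (anticoagulants) and 15 (light-sensitising medication) are, in my judgement, reasons to stop the laser and not reasons to stop counting.

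**4. Size, as illustration only.** Let N = 107 (section 4, the maximum), k the number without a 12-week count under this rule, and gap the difference in mean percent reduction, retained minus lost. Then

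all-treated mean = m_retained + (k/N) × (m_lost − m_retained),

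so a complete-case mean differs from the all-treated mean by (k/N) × gap. Only N comes from the documents; k and gap are assumed. The formula also assumes a complete-case primary mean and no other missing data, neither of which the visible text establishes. For example, 5/107 × 30 = 1.40.

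| k (share of 107) | gap 10 | gap 30 | gap 50 |
|---|---|---|---|
| 0 | 0 | 0 | 0 |
| 1 (0.9%) | 0.09 | 0.28 | 0.47 |
| 5 (4.7%) | 0.47 | 1.40 | 2.34 |
| 11 (10.3%) | 1.03 | 3.08 | 5.14 |

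The figures are percentage points. The reduction is overstated if those lost did worse and understated if they did better.

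**5. Safety.** Sections 4.5.1 and 7.4 tie adverse-event questioning to visits and contacts (the sentence in 4.5.1 runs into a redaction). Leaving before week 4 loses all 3 scheduled post-treatment follow-ups. Leaving just after week 12 loses 1 of 3, and 52 − 12 = 40 weeks of scheduled follow-up. Section 7.5 still follows events already reported, so the gap is confined to new, later events.

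**The case against.** The strongest objection is redaction. The pages after 5.3 are blacked out, no text of section 6 is visible, and most of section 11 is withheld. An early-exit visit or off-treatment follow-up rule may sit there. This stands, and it limits the point to the visible wording of 5.3. A missing-data rule alone would not answer the point, because it cannot recover a count that was never taken; a follow-up rule could.

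The clause is also permissive, retention is the stated preference, and nothing shows how often the discretion would be used. This stands too. A general preference followed by an open list does not secure the 12-week count, but neither does it show that any count will be lost.

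A third objection is that keeping subjects who start an acne drug could credit the drug's benefit to the laser. This is correct if their counts simply enter the primary mean, and the fix has to deal with it. A subject retained after starting a drug gives a flagged count, not the value without the drug.

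A reader might also infer more than the documents support:

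- *That removal is mandatory.* Section 5.3 only permits it.
- *That a subject who clears to grade 0 or 1 meets exclusion criterion 1 and must leave.* Sections 4 and 5.1 tie acne severity to baseline, so nothing here rests on that criterion.
- *That the plan has no follow-up or missing-data provision, or that the result is biased towards the laser.* The first cannot be known through the redactions. The second has no derivable size or sign.

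**Conclusion.** The point holds as a weakness in the visible wording of 5.3. It permits leaving the study, undistinguished from stopping laser, for reasons that can track failure or tolerance. Used before the visit 12 weeks after the final treatment, it can remove the primary count; used at any time, it can end scheduled elicitation of new adverse events.

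The size and direction of any bias are not derivable. The effect is zero if the rule is never used this way, and the illustrative shifts run to 5.14 points only for 11 losses with an assumed 50-point gap. No success criterion or standard deviation is visible, so it cannot be said that any conclusion would change. Confidence is medium, because redacted text may already offset the rule. This is a cheap improvement worth making, not a demonstrated flaw in the result.

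**What to change.** Reword 5.3 so that noncompliance, a serious reaction or a newly developed exclusion criterion ends laser treatment. Apply the same to the investigator's best-interest reason where it concerns only laser exposure; otherwise the same subjects could still leave by that route. A subject who has not withdrawn consent then keeps the 4-, 12- and 52-week visits, counted from the last treatment received, for lesion counts and adverse events. Pregnancy stays under 7.6.

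Record the start date of any prohibited acne medication or procedure. Report the primary result both with the later counts included and with them treated as no improvement or as missing, so that drug effect is not credited to the laser. Flag any count taken while a criterion 10 condition interferes with assessment.

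The cost is protocol wording, a start-date field if the case report form lacks one, and one extra sensitivity analysis. A few off-treatment visits are kept, and some subjects with fewer treatments enter the mean. If the redacted sections already provide this follow-up, a cross-reference in 5.3 is enough.

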16 APR 2021

16. *What is the primary purpose of the following statement?*

10 of 10

The image consists of a series of horizontal bars of varying lengths and positions, creating a stepped, architectural effect. The bars are primarily black on a white background, with some white bars appearing in the center of the image. The bars are arranged in a way that suggests a staircase or a series of levels, with some bars extending beyond the edges of the frame. The overall effect is abstract and geometric.

Confidential and Proprietary

Page 20 of 48

16 APR 2021

Confidential and Proprietary

Page 21 of 48

16 APR 2021

Cutera, Inc.

Protocol # C-20-PAC01

"A Safety and Efficacy Study of a 1726nm Laser for the Treatment of Acne Vulgaris"

7.4 Recording AEs/SAEs and ADEs/SADEs

All AEs/SAEs and ADEs/SADEs will be: (1) evaluated, monitored and tracked from the time of the first study treatment and (2) must be recorded in AE section of the protocol specific case report forms (CRFs). Medical occurrences that begin after enrolling into the study and before administration of study treatment will be recorded on the Medical History section of the CRF, not the AE section.

At each contact with the subject, the Investigator must seek information on AEs/ADEs and SAEs/SADEs by specific questioning and, as appropriate, by examination. AEs/ADEs and SAEs/SADEs may be observed by the Investigator and/or clinical research staff, elicited from the subject and/or family member or volunteered by the subject. All observed and volunteered adverse signs and symptoms, anticipated or unanticipated, regardless of severity or frequency, will be recorded in the CRFs. Included in the description should be the nature of the sign or symptom (including location of the AE/ADE as applicable), the date of onset, date of resolution (duration), the severity, anticipated or unanticipated, the relationship to study treatment or other therapy, the action taken (if any), and the outcome.

All SAEs/SADEs, anticipated or unanticipated, must be reported to the Sponsor as soon as possible (no later than 24 hours after occurrence). The SAE/SADE must be recorded in: (1) the protocol-specific CRF and (2) a written report must be submitted to the Sponsor no later than ten (10) working days after the Investigator first learns of the event. The written report shall include a full description of the event and sequelae, in the format detailed by the Sponsor's SAE/SADE Form. Investigator may be required to submit additional reports to the IRB and to the Sponsor related to SAEs/SADEs.

The Sponsor will immediately conduct an evaluation of any SAE/SADEs per 21 CFR part 812.46(b)(1). If the SAE/SADE is determined to be a USADE, the Sponsor will report results of such evaluation to IRB, FDA and participating Investigators pursuant to 21 CFR part 812.150(b)(1). If the Sponsor determines the USADE presents an unreasonable risk to subjects, the Sponsor will terminate the study or parts of the study presenting that risk pursuant to 21 CFR part 812.46(b)(2).

7.5 Follow-up of Subjects after AEs/ADEs

All reported AEs/ADEs should be followed until resolution. In the unusual circumstance that an AE/ADE has not resolved by the time of the subject's completion of the study, an explanation will be entered on the appropriate CRF and the subject will be referred to his or her primary care provider (unless specified otherwise by the sponsor). Resolutions of events and all events that result in permanent discontinuation from this clinical trial are to be documented on the appropriate CRFs.

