11 STATISTICAL CONSIDERATIONS

11.2 Reported Adverse Events

Adverse events (AE) will be categorized as serious and non-serious, device-related and non-device-related, and anticipated and unanticipated. All reported AEs should be followed until resolution. In the unusual circumstance that an AE has not resolved by the time of the subject's completion of the study, an explanation will be entered on the appropriate CRF.

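### By default, Sections 7.5 and 11.2 do not require the final outcome of a device-related or serious event still open at study completion to be obtained

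*Combined protocol and SAP*

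**What the plan says.** Section 7.5 opens with a general rule: "All reported AEs/ADEs should be followed until resolution". It then states an exception. "In the unusual circumstance that an AE/ADE has not resolved by the time of the subject's completion of the study", two things happen. For the record, "an explanation will be entered on the appropriate CRF". For further care, the default is a hand-off: "the subject will be referred to his or her primary care provider (unless specified otherwise by the sponsor"). The section closes with a documentation rule: "Resolutions of events and all events that result in permanent discontinuation from this clinical trial are to be documented on the appropriate CRFs".

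Section 11.2 restates the general rule and the CRF part of the exception ("In the unusual circumstance that an AE has not resolved by the time of the subject's completion of the study, an explanation will be entered"). It does not mention the referral or the sponsor's option.

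Section 7.4 lists what is recorded for each event, including "the date of onset, date of resolution (duration), the severity, anticipated or unanticipated" and "the relationship to study treatment or other therapy, the action taken (if any), and the outcome".

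Three other places bear on the point. Section 4 puts the last planned visit at 52 weeks after the final treatment, and Section 4.1 puts total participation at up to about 18 months. Section 7.6 takes a pregnant subject out of the study but still follows the pregnancy to its end.

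**The concern.** The exception turns on one fact only: whether the event is open at study completion. It does not ask whether the event is related to the device or serious. A persistent skin effect of the laser and an unrelated minor complaint leave the study in the same way, with a note and a referral. Nothing visible asks the site to find out what happened next, or asks the primary care provider to report back.

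This matters because the study is open-label and single-arm. Sections 4.3 and 11.5 judge safety by an overall review of the reported events, in support of a 510(k) submission. Without a control group, how device effects run their course and whether they resolve carries much of the safety argument. The events the exception reaches are those that last longest or start latest. There is also a subject-care side: the default hands the subject to a provider who may not know the investigational treatment.

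**Working it through.** The documents give no figure on this point, so there is nothing to reproduce. The check is a comparison of the sections, with simple arithmetic on observation time.

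**1. What is captured for an event open at exit.**

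| Item | Event resolved before exit | Event open at exit |
|---|---|---|
| Onset, severity, relationship, action taken (7.4) | Recorded | Recorded |
| Outcome (7.4) | Final outcome | Status at exit |
| Date of resolution (7.4) | Recorded | Not available at exit |
| Explanation on the CRF (7.5, 11.2) | Not needed | Required |
| Later status or resolution | Not needed | No default requirement in the visible text |

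Only the last row is a gap. Status at exit is on file.

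**2. Does the exception separate kinds of event?** No. Section 7.5 refers to AEs/ADEs together and 11.2 to AEs. Section 11.2 does classify events as serious or not, device-related or not, and anticipated or not, so the categories needed for a differentiated rule already exist in the plan.

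**3. Does the protocol follow anyone past exit?** Yes. Section 7.6 does so for pregnancy, with a defined end point. Section 7.5 makes no comparable commitment for unresolved device effects.

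**4. How long is an event observed before the exit rule applies?** For a completer, planned observation is 52 minus the onset week, counted from the final treatment:

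- onset during the treatment period: at least 52 weeks
- onset at week 4: 52 − 4 = 48 weeks
- onset at week 12: 52 − 12 = 40 weeks
- first found at week 52: 52 − 52 = 0 weeks

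Visit windows are redacted, so these are nominal. An effect that begins during treatment falls into the gap only if it is still present about a year after the last exposure. The zero-week case is an event first seen a year after that exposure.

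**5. How many subjects?** The documents give no rate of unresolved events. To gauge the workload of the fix only, an assumed 2% to 5% of the maximum 107 subjects would be 0.02 × 107 = 2.1 to 0.05 × 107 = 5.4, or roughly 2 to 5 subjects. This is an assumption and not an estimate of the gap.

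**The case against.** The other side has a good deal right.

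- *The later outcome is never collected.* A reader might infer this, but the text does not support it. The CRF explanation and the outcome item in 7.4 capture status at exit, and the sponsor may specify something other than referral. What is missing is a default requirement.
- *Section 7.5 contradicts itself.* It does not. The second sentence is an express exception to the first, and 11.2 agrees with it as far as it goes. Nor does the text say that contact with the site ends; that is inferred from the referral.
- *The sponsor decides case by case once the event is known.* The text does not say when or how the sponsor specifies otherwise. What can be said is that no criterion is given.
- *Durations of device effects are biased downward.* This would follow only if open events were analysed as though they had ended at exit. No visible text says so, and most of the safety analysis text is redacted.
- *Follow-up is long.* It is. Fifty-two weeks after the final treatment is a real mitigation, and an effect watched for a year already has an informative status.
- *Serious events have their own route.* Section 7.4 requires a written report covering sequelae within ten working days of the Investigator learning of the event, and allows for further reports. That helps, but the deadline runs from first knowledge and the further reports are not tied to resolution.
- *Other rules may exist.* Sections 7.1 to 7.3 are not visible, so a further follow-up rule cannot be excluded. Section 7.5 is nevertheless the section devoted to this subject, and its visible text points to no other.

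These points narrow the concern. They do not supply a requirement to obtain the final outcome of a device-related or serious event open at exit.

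**Conclusion.** The concern holds in a limited form. The stated exit rule treats device-related and serious events like unrelated minor ones and does not, by default, require their final outcome to be obtained. It is a design choice that can be improved cheaply, not an error or an internal conflict.

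For completers, the size is confined to events still open at about 52 weeks after the final treatment. The number of such events cannot be derived, and no bias in duration is shown. The conclusion assumes that no unseen section already requires continued follow-up.

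A reader might also infer that subjects who leave early, for example after a serious reaction (Section 5.3), lose follow-up well before week 52. The visible text does not say whether study completion includes early exit, so this is an open question and not a finding. The amended wording should settle it.

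**What to change.** Amend 7.5 and 11.2 together, along these lines: *Any ADE, SAE or SADE that is unresolved when the subject exits the study continues to be followed by the site, by phone or visit, until it has resolved or the Investigator judges it stable. The status and its date are entered on the CRF. Referral to a primary care provider is made in addition to this follow-up and does not replace it.*

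Keep the present exit rule for non-serious events that are not device-related. Say in the same place whether exit includes early withdrawal and discontinuation. In the analysis text, state that events still open at last contact are reported as ongoing, with duration treated as censored at that contact. If the redacted text already says this, no change is needed there.

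The cost is a protocol amendment, a few extra site contacts, and a few safety records that stay open after the week-52 visit. Those can be reported as a safety update, so the main database need not wait. The amendment leaves treatment, sample size and the 12-week primary endpoint unchanged.
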